6.2 IMPORTANT PROTOCOL VIOLATIONS

Data discrepancies and deviations from the CTP will be identified for all randomised subjects.

Listings of protocol deviations and of unresolved discrepancies will be provided to be discussed at the combined report planning and database lock meeting (RPM/DBLM), e.g. deviations in drug administration, in blood sampling etc. At this meeting, it will be decided whether the discrepant data can be used as they are or whether the data have to be corrected in the clinical database.

Each protocol deviation must be assessed to determine whether it is an important protocol violation. A protocol violation (PV) is important if it affects the rights or safety of the study subjects or if it can potentially influence the primary outcome measure(s) for the respective subjects in a way that is neither negligible nor in accordance with the study objectives. This last category of important PV forms the basis for the decision of whether a subject does or does not belong to an analysis set. PVs that do not influence the subject's rights and safety or the evaluability of the subjects for the main study objectives are called non-important PVs. These are only considered when checking the trial quality in general.

If any important PVs are identified, they are to be summarized into categories and will be captured in the RPM/DBLM minutes via an accompanying Excel spreadsheet [001-MCS-50-413_RD-02] (2). The following table contains the categories which are considered to be important protocol violations in this trial. If the data show other important PVs, this table will be supplemented accordingly by the time of the RPM/DBLM.

Table 6.2: 1 Important protocol violations

Category /Code	Description
A	Entrance criteria not met
A1	Inclusion criteria violated
A2	Exclusion criteria violated
B	Informed consent
B1	Informed consent not available
B2	Informed consent too late
C	Trial medication and randomisation
C1	Incorrect trial medication taken
C2	Randomisation not followed
C3	Non-compliance
C4	Incorrect intake of trial medication
C5	Improper washout between treatments
D	Concomitant medication
D1	Concomitant medication with the potential to affect the assessment of the trial medication
E	Missing data
E1	Certain violations of procedures used to measure primary or secondary data
F	Incorrect timing¹
F1	Certain violations of time schedule used to measure primary or secondary data
G	Other trial specific important violations
G1	Incorrect intake of meal before administration of treatment
G2	PVs affecting safety and rights

¹ Time deviations will only be flagged as important PV, when leading to exclusion of the entire subject from an analysis set
Source: 'Protocol Violation Handling Definitions' [001-MCS-50-413_RD-01] (3)

6.3 SUBJECT SETS ANALYSED

- Treated set (TS):
This subject set includes all subjects who were dispensed study medication and were documented to have taken at least one dose of investigational treatment.
This is the full analysis set population in the sense of ICH-E9 (1). It is used for safety analyses. (The ECG analyses are performed on the TS, except for the exposure-response analyses, which are performed on the ECGPCS defined below.)

Section 7.3.1 of the CTP: *Plasma concentration data and parameters of a subject will be included in the statistical pharmacokinetic (PK) analyses, if they are not flagged for exclusion due to a protocol violation relevant to the evaluation of PK (to be decided no later than in the Report Planning Meeting) or due to PK non-evaluability (as revealed during data analysis, based on the criteria specified below). Exclusion of a subject's data will be documented in the CTR.*

Relevant protocol violations may be

- *Incorrect trial medication taken, i.e. the subject received at least one dose of trial medication the subject was not assigned to.*
- *Incorrect dose of trial medication taken.*
- *Use of restricted medications.*

Plasma concentrations and/or parameters of a subject will be considered as non-evaluable, if for example

- *The subject experienced emesis that occurred at or before two times median t_{max} of the respective treatment (median t_{max} is to be determined excluding the subjects experiencing emesis).*
 - *The subject experiences emesis at any time during the labelled dosing interval.*
 - *A pre-dose concentration is >5% of the C_{max} value of that subject.*
 - *Missing samples/concentration data at important phases of PK disposition curve.*
- PK parameter analysis set (PKS):
The PK parameter analysis set (PKS) includes all subjects from the TS receiving BI 705564 who provide at least one primary or secondary PK parameter (AUC or C_{max}) that was not excluded according to the description above.
Thus, a subject will be included in the PKS, even if he contributes only one PK parameter value for one period to the statistical assessment (FE part).

It is used for assessment of dose proportionality (SRD parts under fasting and fed conditions) and for assessment of the food effect (FE part and each dose level that was tested under both fasting and fed conditions).

The descriptive analysis of PK concentrations will be based on the ADS ADPC as described at the beginning of [Section 7](#).

Table 6.3: 1 Subject sets analysed

Class of endpoint	Analysis set		
	TS	PKS	ECGPCS
Primary and further safety endpoints (incl. ECG)	X		
ECG endpoints and plasma concentrations used in exposure-response analysis			X
Primary and Secondary PK endpoints		X	
Demographic/baseline endpoints	X		
Important PVs/Disposition	X		
Disposition	X		

6.5 POOLING OF CENTRES

This section is not applicable, because the study was performed in only one centre.

6.6 HANDLING OF MISSING DATA AND OUTLIERS

Handling of missing data and outliers will be performed as described in the CTP, Section 7.4.

The only exceptions where imputation might be necessary for safety evaluation are AE dates. Missing or incomplete AE dates are imputed according to BI standards (see 001-MCG-156_RD-01 (4)).

Missing data and outliers of PK data are handled according to BI standards (see 001-MCS-36-472_RD-01) (5).

If single cardiac cycles of an ECG (out of the generally four) are missing, the arithmetic mean per single ECG will be computed with the reduced (1, 2 or 3) number of cardiac cycles.

If replicate ECG recordings (out of generally three) are missing, the arithmetic means per time-point will be computed with the reduced number (1 or 2) of recordings.

For the classification of the on-treatment QTc/QT intervals into “no new onset” / “new onset” categories, a missing value is obtained only in case that

- (i) all on-treatment values are missing and
- (ii) the baseline value is less than or equal to 500 msec, or missing.

If condition (i) is fulfilled but the baseline value is greater than 500 msec, this case will be categorized as “no new onset”. If baseline is missing and the maximum on treatment QTc interval is greater than 450 msec (or 500 msec for QT interval, respectively), this is classified as a “new onset” in the respective category. If baseline is missing and the maximum QTc interval is less than or equal to 450 msec (or 500 msec for QT interval, respectively), this will be categorized as “no new onset”. If baseline is missing, a QTc/QT interval > 500 msec at any time on treatment will be a notable finding. In case of a missing qualitative ECG finding at baseline, a finding observed on treatment will be categorized as “new onset”.

For placebo subjects the missing plasma concentration values will be replaced by 0 for the exposure response analysis.

6.7 BASELINE, TIME WINDOWS AND CALCULATED VISITS

For laboratory parameters, the baseline value is defined as the last measurement before first trial drug administration in the first treatment period.

For vital signs and PK parameters, the baseline value is defined as the last measurement before trial drug administration in each treatment period.

Section 6.1 of the CTP: *Exact times of measurements outside the permitted time windows will be documented. The acceptable time windows for screening and end of trial examination are given in CTP Flow Chart 1 and CTP Flow Chart 3 for the single rising dose part under fasting and fed conditions, respectively, and CTP Flow Chart 2 for the food effect part.*

Study measurements and assessments scheduled to occur ‘before’ trial medication administration on Day 1 are to be performed and completed within a 3 h-period prior to the trial drug administration (including blank values for PK and biomarkers).

Starting from 72 h post administration a deviation from the scheduled time for PK and biomarker sampling of ± 70 min is acceptable. The biomarker samples planned time Day 6 (single rising dose parts) may be taken on day 5 (up to 26 h earlier).

The acceptable deviation from the scheduled time for vital signs, ECG and laboratory tests will be ± 15 minutes for the first 4 hours after trial drug administration and ± 30 minutes thereafter. Starting from 72 h post administration a deviation from the scheduled time for vital signs, ECG and laboratory tests of ± 70 min is acceptable.

Adherence to time windows will be checked via the consistency check listings at the RPM/DBLM.

For the SRD parts under fasting and fed conditions, there will be a centralised evaluation of the 12-lead ECG recordings at the time points and for the ECG recordings specified in the [Table 6.7: 1](#) below:

Table 6.7: 1 Time schedule of 12-lead ECG recordings (SRD part)

Visit	Day	Planned time [hh:mm] (relative to drug administration)	Study phase	Central evaluation
1	-21 to -1		Screening	NA
2	1	-02:00	Baseline	triplicate ECG
		00:30	On treatment	first of three replicate ECG
		01:00		first of three replicate ECG
		01:30		first of three replicate ECG
		02:00		first of three replicate ECG
		03:00		first of three replicate ECG
		04:00		first of three replicate ECG
		06:00		first of three replicate ECG
		08:00		first of three replicate ECG
	12:00	first of three replicate ECG		
	2	24:00	first of three replicate ECG	
	3	48:00	first of three replicate ECG	
4	72:00	first of three replicate ECG		
4	11 to 15		End of trial examination	NA

Triple ECGs will be recorded (three single ECGs within 180 sec) at all time points in Visit 2. At Visits 1 and 4, single ECGs will be recorded.

Section 5.2.4.1 of the CTP: *With the exception of the first triple ECG (used as baseline before the first drug administration), only the first of the three replicate ECGs at a single assessment time will be evaluated.*

The baseline value of an ECG variable is defined as the mean of the 3 triplicate ECG measurements prior to drug administration.

For the exposure response analyses, pairs of ECG measurements and corresponding plasma concentrations will be built using the same time points, e.g. HR change from baseline and

plasma sample taken at planned time 0:30 will build one pair. Whether a time deviation between PK blood sampling time and corresponding ECG recording is too big and the pair has to be excluded will be decided no later than at the RPM. This critical time deviation depends on the PK properties. When plasma concentrations are expected to change only little around a given time point, the time deviation between ECG recording and PK blood sampling can be bigger.

For the FE part, no centralised evaluation of all 12-lead ECG recordings is planned.

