**(2) Food effect part**

Visit	Day	Planned time (relative to drug administration) [h:min]	Approximate clock time of actual day [h:min]	Event and comment	Safety laboratory	PK  blood	12-lead ECG	Vital signs (BP, PR)	Questioning for AEs and concomitant therapy 
1	-21 to -1			Screening (SCR) 	x		x 	x	
2/ 3*	-3 to -1	-72:00 	08:00	Ambulatory visit	x				x
	1	-2:00	06:00	Admission to trial site  , allocation to treatment  (Visit 2 only)	x 	x 	x 	x 	x 
		-0:30	07:30	High fat, high calorie breakfast (only in treatment 'fed')					
		0:00	08:00	Drug administration					
		0:30	08:30			x			
		1:00	09:00			x	x 	x	x
		1:30	09:30			x			
		2:00	10:00	240 mL fluid intake		x	x 	x	x
		3:00	11:00			x			
		4:00	12:00	240 mL fluid intake, thereafter lunch 		x	x 	x	x
		6:00	14:00			x			x
		8:00	16:00	Snack (voluntary) 		x	x 	x	x
		10:00	18:00			x			
		11:00	19:00	Dinner					
		12:00	20:00			x			x
	2	24:00	08:00	Discharge from trial site, breakfast  (voluntary)	x	x	x 	x	x
		34:00	18:00	Ambulatory visit		x			x
	3	48:00	08:00	Ambulatory visit		x			x
	4	72:00	08:00	Ambulatory visit		x			x
4	11 to 15			End of trial (EOT) examination 	x		x 	x	x

\* Two identical visits, separated by a wash-out interval of at least 10 days between drug administrations

1. Subject must be informed and written informed consent obtained prior to starting any screening procedures. Screening procedures include physical examination, check of vital signs, ECG, safety laboratory (including drug screening), demographics (including determination of body height and weight, smoking status and alcohol history), relevant medical history, concomitant therapy and review of inclusion/exclusion criteria. Pharmacogenetic samples will be collected, if needed.
2. The time is approximate. The respective procedure is to be performed and completed within 3 h prior to drug administration. Allocation to treatment may be performed at any time following enrolment but must be completed prior to the first drug administration.
3. If several actions are indicated at the same time point, the intake of meals will be the last action.

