4. End of trial examination includes physical examination, vital signs, ECG, safety laboratory, recording of AEs and concomitant therapies.
5. Only urine drug screening and alcohol breath test
6. AEs and concomitant therapies will be recorded throughout the trial, but will be specifically asked for at the time points indicated in the Flow Chart.
7. The ECG will be recorded as single ECG. However, the number of ECGs per time point may be increased to three ECGs based on the preliminary ECG results obtained during the single rising dose part.
8. Sampling times may be adapted based on information obtained during the trial (e.g. preliminary PK data) including addition of samples and visits as long as the total blood volume taken does not exceed 500 mL per subject.
9. Safety laboratory to be taken and medically evaluated within 3 days prior to administration of study drug. This ambulatory visit, including safety laboratory, can be omitted in visit 2, if the screening examination is performed on Days -3, -2 or -1.

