### 3. DESCRIPTION OF DESIGN AND TRIAL POPULATION

#### Global Amendment No 4 – major changes in Section 3:

Originally, the study was planned to consist of two study parts: (1) SRD part under fasting conditions consisting of 8 dose groups (1 to 160 mg) à 8 volunteers (64 volunteers in total) and (2) food effect part investigating the effect of a high-fat, high-calorie breakfast on doses of 10 mg and 40 mg in 12 volunteers each, i.e. in 24 volunteers total.

Data obtained during the trial indicate that no relevant increase of exposure was to be expected with dose groups 120 mg and 160 mg in the SRD part under fasting conditions. Therefore, the two highest dose groups of the SRD part under fasting conditions (120 mg and 160 mg) are not dosed. Data of the food effect part 10 mg indicate that relative bioavailability of BI 705564 tablet may be increased by food. The food effect part 40 mg is not dosed. Instead, a third study part is added. A SRD part under fed conditions is added to the study and is designed to investigate single rising oral doses of BI 705564 after a high-fat, high-calorie breakfast. It is planned to apply BI 705564 to 4 dose groups à 8 volunteers per group (32 volunteers in total) with the possibility to add up to 2 interim dose groups in the SRD part under fed conditions (see Section 3.1, “Single rising dose part under fed conditions”).

See [Appendix 11](#) for details.

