### 5.2.3 Assessment of safety laboratory parameters

For the assessment of laboratory parameters, blood and urine samples will be collected by the trial site at the time points indicated in the [Flow Charts](#) after the subjects have fasted for at least 10 h. Overnight fasting is not required at the discretion of the investigator or designee for retests or drug screening. In the single rising dose part under fed conditions, fasting is not applicable to the post-dose safety laboratory on Day 1.

The parameters that will be determined are listed in Tables 5.2.3: 1 and [5.2.3: 2](#). Reference ranges will be provided in the ISF, Section 10.

Manual differential white blood cell count or urine sediment examinations will only be performed, if there is an abnormality in the automatic blood cell count or in the urinalysis, respectively.

Table 5.2.3: 1 Routine laboratory tests

Functional lab group	Test name	SCR	A 	B 	C 	EOT
Haematology	Haematocrit	x	x	x	x	x
	Haemoglobin	x	x	x	x	x
	Red blood cell count (RBC)	x	x	x	x	x
	Reticulocyte count	x	--	--	x	x
	White blood cell count (WBC)	x	x	x	x	x
	Platelet count	x	x	x	x	x
Automatic WBC differential (relative and absolute)	Neutrophils, eosinophils, basophils, monocytes, lymphocytes	x	x	x	x	x
Manual differential WBC (if automatic differential WBC is abnormal)	Polymorphnuclear neutrophils (segs), band neutrophils (stabs), eosinophils, basophils, monocytes, lymphocytes					
Lymphocyte differentiation (relative and absolute; except for ratio)	T cells (CD3+), T helper cells (CD3+CD4+), cytotoxic T cells (CD3+CD8+), B cells (CD19+), natural killer cells (CD16+CD56+CD3-), double-positive T cells (CD3+CD4+CD8+), CD4:CD8 ratio	x	--	--	x 	x
Serum immunoglobulins	IgA	x	--	--	x	x
	IgG	x	--	--	x	x
	IgM	x	--	--	x	x
Coagulation	Activated partial thromboplastin time (aPTT)	x	x	x	x	x
	Prothrombin time (Quick's test and INR)	x	x	x	x	x
	Fibrinogen	x	--	x	x	x

 A: Days -3 to -1

 B: post-dose on Day 1 (single rising dose parts)

 C: Days 2, 3, 8 (single rising dose parts) and Day 2 (food effect part)

 Not on Day 3 (single rising dose parts)

Table 5.2.3: 1 Routine laboratory tests (cont'd)

Functional lab group	Test name	SCR	A 	B 	C 	EOT
Enzymes	Aspartate transaminase (AST/GOT)	x	x	x	x	x
	Alanine transaminase (ALT/GPT)	x	x	x	x	x
	Alkaline phosphatase (AP)	x	--	x	x	x

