Adverse events will be coded using the Medical Dictionary for Regulatory Activities (MedDRA). Frequency, severity and causal relationship of AEs will be tabulated by treatment, system organ class and preferred term. SAEs, AESIs (see [Section 5.2.2.1](#)) and other significant AEs (according to ICH E3) will be listed separately.

Laboratory data will be compared to their reference ranges. Values outside the reference range as well as values defined as clinically relevant will be highlighted in the listings. Additionally, differences from baseline will be evaluated.

Vital signs or other safety-relevant data observed at screening, baseline, during the course of the trial and at the end-of-trial evaluation will be assessed with regard to possible changes compared to findings before start of treatment.

For the single rising dose parts (under fasting and fed conditions) of the study, a centralised evaluation of all 12-lead ECGs recordings (see [Section 5.2.4](#)) will be the basis for the derivation of further ECG parameters based on the ECG variables QT, HR, QTcF, QTcB, PR, QRS, and RR. The baseline value of an ECG variable is defined as the mean of the triple ECG measurements prior to drug administration. The derivation of the quantitative and qualitative ECG endpoints and their analyses will be described in the TSAP.

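### In the food effect crossover, laboratory changes in period 2 are measured from before dose 1 but tabulated under the period 2 treatment; for 29 of 44 test rows a period-specific baseline is available at little cost

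*SAP*

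**What the plan says.** SAP 6.7 gives two baseline rules. For laboratory tests: "For laboratory parameters, the baseline value is defined as the last measurement before first trial drug administration in the first treatment period." The next sentence reads: "For vital signs and PK parameters, the baseline value is defined as the last measurement before trial drug administration in each treatment period." No reason is given for the difference. Each subject in a single rising dose part receives one dose, so the wording about a first period only has an effect in the food effect part.

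The other relevant provisions are:

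- **Design.** Flow Chart 2 describes the food effect periods as follows: "Two identical visits, separated by a wash-out interval of at least 10 days between drug administrations."
- **Attribution.** Protocol 7.3.4 assigns measurements to the actual treatment at the planned time. SAP 6.1 tabulates laboratory values by on-treatment phase; in the food effect part the period 1 phase ends at the second dose.
- **Analysis.** On laboratory data, protocol 7.3.4 states: "Additionally, differences from baseline will be evaluated." SAP 7.8.2 describes only comparison with reference ranges and the handling of clinically significant values, but SAP 4 declares that every analysis planned in the protocol will be done.
- **Sampling.** Flow Chart 2 schedules a safety laboratory on Days -3 to -1 of both periods. Footnote 9 says: "This ambulatory visit, including safety laboratory, can be omitted in visit 2, if the screening examination is performed on Days -3, -2 or -1." It grants no such exemption for Visit 3.

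**The concern.** The label and the reference point do not match. A period 2 laboratory change carries the name of the second treatment but covers everything since before the first dose. If something from period 1 is still present, the table shows it as a change under the wrong meal condition. The residual effect period is stated to be unknown in this first-in-human trial (protocol 5.2.2.2), so full recovery within the washout cannot simply be assumed. A lasting shift need not be a drug effect either: period 1 also involves repeated blood sampling.

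At stake is how the descriptive laboratory tables read by treatment. Safety and tolerability are an additional objective of this part (protocol 7.1.1).

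**Working it through.** **The plan's own figure.** The plan gives no figure on laboratory change. The only computed figures for this part are the precision values in protocol Table 7.6: 1. They reproduce as exp(t(0.95; 10) × √ln(1+gCV²) × √(χ²(0.95; 10)/10) × √(2/12)) = 1.2193, 1.2795 and 1.3416 for gCV 20, 25 and 30%, against 1.22, 1.28 and 1.34 stated. They do not depend on the laboratory baseline.

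**Step 1: size of the misattribution.** Inputs: 12 subjects (protocol 7.6), allocated 1:1 (protocol 7.5), so 6 in fed-then-fasting and 6 in fasting-then-fed. Let cT be the shift from the pre-dose-1 value still present at the period 2 laboratory sample in subjects dosed fed first, and cR the same for those dosed fasting first. With the fixed baseline:

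- error in mean change, fasting = (6 × 0 + 6 × cT)/12 = cT/2
- error in mean change, fed = (6 × 0 + 6 × cR)/12 = cR/2
- error in fed minus fasting = (cR − cT)/2
- error in one subject's period 2 change = the full cT or cR

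The shifts below are assumed, in arbitrary units:

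| Sequences | cT | cR | Fed | Fasting | Fed − fasting |
|---|---|---|---|---|---|
| 6:6 | 0 | 0 | 0 | 0 | 0 |
| 6:6 | 1 | 1 | +0.5 | +0.5 | 0 |
| 6:6 | 1 | 0.5 | +0.25 | +0.5 | −0.25 |
| 6:6 | 1 | 0 | 0 | +0.5 | −0.5 |
| 6:3 | 1 | 1 | +0.333 | +0.667 | −0.333 |

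The last row has nine subjects with data in both periods, six of them fed first. Equal shifts cancel in the contrast only while the sequences are balanced.

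**Step 2: a source other than the drug.** Flow Chart 2 has 15 pharmacokinetic samples per period (pre-dose plus 14 from 0:30 to 72:00), each 2.7 mL (protocol 5.5.2.1): 15 × 2.7 = 40.5 mL before the second period, besides the safety bloods. Any resulting fall in blood count would enter the period 2 change. The documents do not quantify it.

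**Step 3: which tests have a period 2 pre-dose value.** Rows of protocol Table 5.2.3: 1, Day 2 (column C) against Days -3 to -1 (column A):

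| Group | C | A |
|---|---|---|
| Haematology | 6 | 5 |
| Automatic differential | 1 | 1 |
| Lymphocyte differentiation | 1 | 0 |
| Immunoglobulins | 3 | 0 |
| Coagulation | 3 | 2 |
| Enzymes | 9 | 6 |
| Substrates | 9 | 4 |
| Electrolytes | 3 | 2 |
| Urinalysis | 9 | 9 |
| **Total** | **44** | **29** |

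The 44 − 29 = 15 rows without a scheduled period 2 pre-dose value are reticulocytes, lymphocyte differentiation (with CD19+ B cells), IgA, IgG, IgM, fibrinogen, alkaline phosphatase, GLDH, CK, glucose, total protein, uric acid, cholesterol, triglycerides and calcium. For these, the last scheduled value before dose 2 is Day 2 of period 1, about 24 h after dose 1.

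**Step 4: is the period-specific baseline clean?** The pre-dose sample precedes the Day 2 sample by about 2 to 4 days. If the residual is c at the pre-dose sample and r × c on Day 2, the fixed baseline errs by r × c and the period baseline by (r − 1) × c. For c = 1: r = 1 gives 1 and 0; r = 0.75 gives 0.75 and −0.25; r = 0.5 gives 0.5 and −0.5; r = 0.25 gives 0.25 and −0.75. Below r = 0.5 the period baseline errs more, in the opposite direction.

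**The case against.** The best defence is that the fixed baseline is a deliberate and reasonable choice. The protocol sets no laboratory baseline, so the SAP breaks no rule. The value before dose 1 is the only drug-free reference and keeps lasting or cumulative change visible. The sample before dose 2 belongs to the period 1 on-treatment phase under SAP 6.1, and step 4 shows that it can be the worse reference for a fast-decaying residual. One rule for all tests is also simpler than two. All of this stands, and it is why the pre-first-dose baseline should be kept alongside, not replaced.

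It also stands that little depends on the choice. The analysis is descriptive, the reference-range comparison uses no baseline, no fed-fasting laboratory difference is specified for estimation, and individual values are listed by visit, so a shifted pre-dose value can be seen. The sponsor's laboratory standard cited in SAP 7.8.2 may add detail not visible here.

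The defence does not explain why vital signs in the same crossover are treated differently. Nor does the silence of SAP 7.8.2 on change from baseline remove the analysis, since SAP 4 retains the protocol's plan.

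A reader might go further and infer that the fed-fasting laboratory comparison is biased toward zero because the fed dose leaves the larger residual. The documents do not support that. On exposure the protocol says only: "Data of the food effect part 10 mg indicate that relative bioavailability of BI 705564 tablet may be increased by food." Both treatments are the same single 10 mg tablet, protocol 2.3.2.2 considers on-target effects unlikely after one dose, and no residual at 10 days or later is reported. Unequal residuals are possible, not shown.

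**Conclusion.** The point holds as a limited one. SAP 6.7 measures period 2 laboratory change from before dose 1 while the tables attribute it to the period 2 treatment. The error is zero without a lasting shift. Otherwise it is half the shift in the affected treatment's mean change, the full shift in an individual's period 2 change, and (cR − cT)/2 in the contrast with 6:6 sequences. These results rest on complete data in both periods and on shifts for which the documents give no values.

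Two stronger readings should be avoided. It is not the case that every laboratory change after dose 1 is charged to the other treatment; only what outlasts the washout of at least 10 days is. And although every subject entering period 2 should have a pre-dose safety laboratory, it does not cover every test: the on-target markers, CD19+ B cells and immunoglobulins, are among the 15 rows not covered. The pharmacokinetic results, sample size and precision are untouched. This is a cheap improvement to a descriptive display in 12 subjects.

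**What to change.** In SAP 6.7, for the food effect part:

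1. For the 29 column A rows of protocol Table 5.2.3: 1, define the laboratory baseline as the last measurement before drug administration in each treatment period, as already done for vital signs.
2. Keep the change from the pre-first-dose value as a second display for period 2, so that a lasting change stays visible and a reader can see where the two references disagree.
3. For the 15 other rows, keep the first-period baseline and mark it as such in the table. Do not let a rule based on the last value before dosing pick up Day 2 of period 1.
4. State in SAP 7.8.2 that differences from baseline are produced, and by which definition.

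The cost is a few sentences and one additional derived variable, using samples the protocol already schedules. The downside is two change columns for period 2 and two baseline definitions within one table. If the sponsor prefers the single baseline, a stated reason for departing from the vital-signs rule is the minimum.
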